evidence for a causal relation between tetanus toxoid-containing vaccines and brachial neuritis (32). Arthus reactions are rarely reported after vaccination and can occur after tetanus toxoid-containing vaccines (33).

No occurrences of GBS, brachial neuritis, or Arthus reaction have been reported with the use of MenACYW conjugate vaccine in the completed clinical trials.

The risk of vasovagal syncope exists after any vaccination in the adolescent age group. A few cases of immediate vasovagal-like response or syncope have been observed in adolescent subjects who had received MenACYW conjugate vaccine. Syncope has been reported following vaccination with Menactra®. Procedures should be in place to prevent falling injury and manage syncopal reactions.

The potential risks associated with blood drawing include local pain, bruising, and, rarely, fainting.

The potential risk listed here are not exhaustive. Refer to the package insert of Menactra® (34) and the Investigator's brochure (IB) for the investigational vaccine for additional information regarding the potential risks.

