5 INVESTIGATIONAL PLAN

5.1 DESCRIPTION OF THE OVERALL STUDY DESIGN AND PLAN

5.1.1 Study Design

This will be a Phase III, modified double-blind, randomized, parallel-group, active-controlled, multi-center study to evaluate immune non-inferiority of MenACYW conjugate vaccine versus Menactra® and describe the safety and additional immunogenicity of the study vaccines in children (2-9 years of age), adolescents (10-17 years of age) and adults (18-55 years of age) in Japan. Approximately 360 healthy children, adolescents and adults will be stratified and randomly assigned in a 1:1 ratio to the following groups:

- Group 1 (investigational): MenACYW conjugate vaccine (180 subjects)
- Group 2 (control): Menactra® (180 subjects)

All subjects will provide blood samples for immunogenicity assessment at baseline (pre-vaccination) and at 30 days post-vaccination.

Solicited injection site and systemic reactions will be collected for 7 days after vaccination, unsolicited AEs will be collected from Visit 1 (D0) to Visit 2 (D30 [+14 days]), and SAEs will be collected from signing of the informed consent at D0 through D30 (+14 days) after vaccination.

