5.1.4 Visit Procedures

Medical procedures (examinations, injections, etc.) must be conducted by appropriately licensed or credentialed study site staff working within the scope of their license/credentials.

Visit 1 (D0): Inclusion, Randomization, Blood Sample, and Vaccination

1. Give the subject and/or the subject's parent / legally acceptable representative information about the study, answer any questions, obtain written informed consent and assent (as applicable) and give the subject or subject's parent / legally acceptable representative a signed copy of the ICF and a signed copy of the assent form (as applicable).

- Subjects 2 to 6 years of age: ICF signed by the subject's parent / legally acceptable representative
- Subjects 7 to 19 years of age: assent form signed by the subject and ICF signed by the subject's parent / legally acceptable representative
- Subjects 20 to 55 years of age: ICF signed by the subject

2. Check inclusion and exclusion criteria for eligibility (see [Section 5.2.4](#) and [Section 5.2.5](#), respectively).
3. Collect relevant demographic information.
4. Perform urine pregnancy test (if applicable).
5. Obtain verbal medical history about the subject.
6. Conduct a history-directed physical examination, including temperature (preferably axillary temperature). A physical examination conducted during the same day as part of routine clinical care may be used for this purpose.
7. Contact the interactive response technology (IRT) for subject identification number and vaccine dose number (see [Section 6.5](#) for instructions).
8. Obtain the first blood sample (5 milliliter [mL]) (see [Section 7](#) for detailed instructions regarding the handling of blood samples). If attempts to obtain the first blood draw are unsuccessful (no more than 3 attempts), then Visit 1 can be rescheduled to a later date at which point informed consent and inclusion/exclusion criteria must be re-validated. If the first blood draw cannot be obtained, the subject will be withdrawn from the study without being vaccinated.
9. Administer the appropriate study vaccine to the subject in the deltoid muscle. The vaccine must be administered on the side opposite to that of the blood sampling.

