5.4.2.2 Unsolicited Non-serious AEs

Presence

An observation will be considered an event if it has at least a verbatim term and is not a Grade 0 intensity event. Grade 0 events should be included in the listing “Unsolicited non-serious adverse events not included in the safety analysis.”

Intensity

Intensity for unsolicited non-serious AE will be derived according to the following classification: None: Grade 1, Grade 2, Grade 3, or Missing. The category of Unknown will be considered Missing if Unknown is recorded as well as the intensity classification of solicited reactions.

If the unsolicited non-serious AE is measurable and its preferred term is part of the list of solicited reactions, then the measurement is derived based upon and following the same rule than the intensity scales defined in the protocol for that measurable injection site or systemic reaction.

Intensity for the other unsolicited non-serious AEs will correspond to the value reported in the CRF.

The maximum intensity corresponds to the highest intensity for a unique term.

Last vaccination

Last vaccination before any unsolicited non-serious AE is the study vaccination at Visit 1.

Time of onset

Time of onset is derived from the start date of the unsolicited non-serious AE provided in the clinical database and the date of last vaccination:

start date of the unsolicited non-serious AEs – date of previous vaccination

The time of onset should be considered as missing only if one or both of the dates are missing or partially missing.

The unsolicited non-serious AEs will be analyzed “Within 30 days”, which corresponds to AEs with a time of onset between 0 and 30 days after vaccination or missing. An AE with missing time of onset will be considered to have occurred just after the vaccination indicated by the visit number, so will be included in these tables.

Note: Unsolicited non-serious AEs that occurred before vaccination (negative time of onset) or with a time of onset higher than defined above will not be included in analysis, but will be listed separately.

Duration

Duration is derived from the start and stop dates of the unsolicited non-serious AE provided in the clinical database:

stop date of unsolicited non-serious AE – start date of unsolicited non-serious AE + 1.

The duration should be considered as missing only if one or both of the start and stop dates of the unsolicited non-serious AE is missing or partially missing.

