5.4.2.3 SAEs

Last vaccination

The last vaccination before any SAE is defined as the study vaccination at Visit 1.

Time of onset

Time of onset will be computed using the same methodology than for unsolicited non-serious AEs described in [Section 5.4.2.2](#).

SAEs will be analyzed throughout the study using the following periods:

- During the study (i.e., all SAEs occurred during the study)
- Within 30 days after vaccination

An SAE with missing time of onset will be considered to have occurred just after the vaccination indicated by the visit number, so will be included in these tables.

Note: SAEs that occurred before vaccination (negative time of onset) will not be included in analysis, but will be listed separately.

Duration

Duration will be computed using the same methodology than for unsolicited non-serious AEs described in [Section 5.4.2.2](#).

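### The date-only time-of-onset rule counts AEs and SAEs that start on Day 0 before the injection as post-vaccination, contrary to the SAP's own note (minor)

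*SAP*

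**What the plan says.** SAP 5.4.2.2 computes time of onset as "start date of the unsolicited non-serious AEs – date of previous vaccination". This is a difference of dates with no clock time. The within-30-days analysis takes events with "time of onset between 0 and 30 days after vaccination or missing", so a value of 0 is in. A note then deals with "Unsolicited non-serious AEs that occurred before vaccination (negative time of onset"), which are to be kept out of the analysis and listed separately.

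SAP 5.4.2.3 uses the same derivation for SAEs and repeats the note: "SAEs that occurred before vaccination (negative time of onset) will not be included in analysis, but will be listed separately".

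Protocol 5.1.4 puts the relevant steps in a single visit, headed "Visit 1 (D0): Inclusion, Randomization, Blood Sample, and Vaccination". Consent is step 1, the bleed is step 8 and the injection is step 9. The Table of Study Procedures confirms that blood is drawn before the vaccine is given.

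Collection starts before the injection, at least for SAEs. Protocol 5.1.1 says that "SAEs will be collected from signing of the informed consent at D0", and that unsolicited AEs are collected from Visit 1. Protocol 9.2.2.3.3, by contrast, asks subjects to record events in the period after vaccination.

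**The concern.** The SAP intends that events which began before the vaccine do not appear in the AE tables. Its operational test for that is a negative date difference. In the usual course of this trial the whole interval between consent and injection falls on the vaccination date, so the test has nothing to act on there.

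Such events are foreseeable. Protocol 1.3.2 states: "The potential risks associated with blood drawing include local pain, bruising, and, rarely, fainting". The same section names vasovagal syncope as a risk after vaccination, so a faint at the bleed and a faint after the injection look alike if only the date is known. The causality definition in Protocol 9.2.2.3.4 also allows for an AE that began before vaccination.

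At stake are the absolute frequencies of unsolicited AEs and SAEs reported for each vaccine. The endpoints in Protocol 9.2.2.2 describe these as events after vaccination.

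**Working it through.** The plan states no figure on this point, so there is none to reproduce. The check applies the rule to test cases and then shows a range for the size.

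**Inputs.** Onset = start date − vaccination date (SAP 5.4.2.2, adopted in 5.4.2.3). For non-serious AEs, the event is counted if onset is 0 to 30 or missing, and listed separately if negative or above 30. For SAEs, negative onset is listed separately, and the periods are within 30 days and the whole study. Planned group size is 180, total 360 (SAP 2).

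**Rule applied to a non-serious AE:**

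| Event | Onset | Result |
|---|---|---|
| Day 0, before or at the bleed | 0 | counted |
| Day 0, after the injection | 0 | counted |
| Day before the injection (Visit 1 rescheduled) | −1 | listed separately |
| Day 30 | 30 | counted |
| Day 31 | 31 | listed separately |

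The first two rows get the same value, so the rule cannot separate them. The third row shows that it works for an earlier date. Protocol 5.1.4 allows that case: after unsuccessful draws Visit 1 may move to a later day, with consent re-validated. An SAE on Day 0 before the injection also gets 0 and enters both SAE periods.

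**Is the event recorded at all?** For SAEs, yes: collection runs from consent. For non-serious events the texts differ. Protocol 5.1.1 says from Visit 1. In Protocol 5.1.4, however, the AE-recording step (step 10) and the handing out of the diary card (step 11) both follow the injection, and 9.2.2.3.3 refers to the period after vaccination.

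**Size, under assumption.** Let r be the proportion of subjects with a recorded event that starts on Day 0 before the injection. The documents give no value for r.

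- Expected subjects per group = 180 × r.
- P(at least one in 360) = 1 − (1 − r)^360.
- SD of the chance difference between groups = √(2r(1 − r)/180).

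| Assumed r | Subjects per group | P(at least one in 360) | SD of difference, percentage points |
|---|---|---|---|
| 0.5% | 0.9 | 0.84 | 0.7 |
| 1% | 1.8 | 0.97 | 1.0 |
| 2% | 3.6 | 0.999 | 1.5 |
| 5% (deliberately high) | 9.0 | >0.999 | 2.3 |

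The expected difference between groups is zero at every r, because the events precede vaccination in a 1:1 randomized trial. If sites do not record pre-injection non-serious events, r for those events is zero and only SAEs remain.

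**The case against.** The strongest reply is that the rule will rarely misfire.

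- The working procedures for non-serious AEs mostly start after the injection, and the endpoint itself is worded as after vaccination. This stands in part. It makes capture uncertain, but the Visit 1 wording in Protocol 5.1.1 is left unreconciled.
- A subject with an SAE between consent and injection would probably not be vaccinated, given exclusion E 18 on acute illness that day, and would then fall outside the SafAS. This stands as a reason to expect very few such SAEs.
- An AE that began before vaccination is by definition not related (Protocol 9.2.2.3.4), so it should stay out of the adverse-reaction tables. This stands unless causality is missing, which SAP 5.4.4.1 treats as related.
- Over-counting is the cautious direction, and SAP 4.7 makes the safety analysis descriptive without tests. This stands and limits the weight of the point. It does not reconcile the rule with its own note.

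A reader might infer more than the documents support:

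- *That the rule cannot remove any pre-vaccination event.* It removes every event dated before the injection day.
- *That every event between consent and injection is counted.* It is counted only if it is recorded, and a bleed-related event that begins after the injection is properly a post-vaccination AE.
- *That bleed events would swell the immediate AE count, for example against the low rate in MET43.* Immediate events are those in the 30 minutes after vaccination. Non-serious ones are identified from a CRB field (Protocol 9.2.2.3.1, SAP 5.4.4.1), not from the date difference, so that comparison is not valid.

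**Conclusion.** The point holds, and it is minor. For an event on the vaccination date, the SAP's definition of pre-vaccination does not do what its note says: a recorded AE or SAE that began before the injection is tabulated within 30 days and, for SAEs, also during the study. This is a stated rule that gives the wrong class, not a missing detail.

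The number of subjects affected cannot be had from the documents and is likely small. The estimate of roughly 1 to 4 per group rests on assumed rates of 0.5% to 2%, and on pre-injection events being recorded. The protocol itself calls fainting at the bleed rare. The effect has no expected difference between groups. It bears only on descriptive safety frequencies, and it leaves the primary immunogenicity analysis untouched.

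**What to change.** Amend the notes in SAP 5.4.2.2 and 5.4.2.3. An event with onset 0 is treated as pre-vaccination, and listed separately, when source documents show that it began before the injection. Record this with a before/after-injection flag set at the blind data review that Protocol 11.3 already plans before database lock.

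Keep two kinds of Day 0 event in the tables: those whose timing relative to the injection is unknown, and bleed-related events that begin after it. Do not use the relationship-to-study-procedures field to decide timing. It records causality, and using it could remove a genuine post-vaccination SAE.

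Also align Protocol 5.1.1 with 9.2.2.3.3 on when collection of non-serious AEs starts.

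The cost is one added sentence in each of the two SAP sections, one flag, a clarification of the collection start, and a few queries on Day 0 events before lock.

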5.4.2.3 SAEs

Last vaccination

The last vaccination before any SAE is defined as the study vaccination at Visit 1.

Time of onset

Time of onset will be computed using the same methodology than for unsolicited non-serious AEs described in [Section 5.4.2.2](#).

SAEs will be analyzed throughout the study using the following periods:

- During the study (i.e., all SAEs occurred during the study)
- Within 30 days after vaccination

An SAE with missing time of onset will be considered to have occurred just after the vaccination indicated by the visit number, so will be included in these tables.

Note: SAEs that occurred before vaccination (negative time of onset) will not be included in analysis, but will be listed separately.

Duration

Duration will be computed using the same methodology than for unsolicited non-serious AEs described in [Section 5.4.2.2](#).

5.4.2.4 Other Safety Endpoints

Pregnancy

This information will be listed as collected. No derivation or imputation will be done.

Action taken

This information will be summarized as collected, including missing observation. No derivation or imputation will be done.

Seriousness

This information will be summarized as collected. No derivation or imputation will be done.

Outcome

This information will be summarized as collected. No derivation or imputation will be done.

Causality

This information will be summarized as collected. Missing causality (relationship) will be handled as described in [Section 5.4.4.1](#).

AEs leading to study discontinuation

A flag is available in the clinical database for all AEs in order to identify AEs leading to discontinuation.

In general, the items that are counted are:

- Disposition table: A subject who has, on the termination form, the reason for early termination “Adverse Event” is checked.
- Safety overview table: A subject who has either on the termination form the reason for early termination “Adverse Event” is checked or lists an AE on an AE page (solicited, unsolicited) that has “Caused Study Termination” checked that is at least Grade 1 and is within the time period indicated.
- System Organ Class/Preferred Term (SOC/PT) table: An event (solicited, unsolicited, or SAE) that has “Caused Study Termination” checked that is at least Grade 1 and is within the time period indicated.

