5.2.9 Conditions for Withdrawal

Subjects and/or subjects' parents / legally acceptable representatives will be informed that they have the right to withdraw from the study at any time. A subject may be withdrawn from the study:

- At the discretion of the Investigator or Sponsor due to safety concerns or significant non-compliance with the protocol (based on the Investigator's judgment), without the subject's or subject's parent's / legally acceptable representative's permission (withdrawal)
- At the request of the subject or subject's parent / legally acceptable representative (dropout)

The reason for a withdrawal or dropout should be clearly documented in the source documents and in the CRB.

The Investigator must determine whether voluntary withdrawal is due to safety concerns (in which case, the reason for discontinuation will be noted as "Adverse Event") or for another reason.

Withdrawn subjects will not be replaced.

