9.2.2.2 Safety Endpoints

The secondary endpoints for the evaluation of safety are:

- Occurrence, nature (Medical Dictionary for Regulatory Activities [MedDRA] preferred term), duration, intensity, and relationship to vaccination, of any unsolicited systemic AEs reported in the 30 minutes after vaccination.
- Occurrence, time to onset, number of days of occurrence, intensity, action taken, and whether the reaction led to early termination from the study, of solicited (prelisted in the subject's diary card and CRF) injection site reactions occurring up to 7 days after vaccination.
- Occurrence, time to onset, number of days of occurrence, intensity, action taken, and whether the reaction led to early termination from the study, of solicited (prelisted in the subject's diary card and CRF) systemic reactions occurring up to 7 days after vaccination.
- Occurrence, nature (MedDRA preferred term), time to onset, duration, intensity, action taken, relationship to vaccination (for systemic AEs only), and whether the event led to early termination from the study, of unsolicited AEs up to Visit 2 after vaccination.
- Occurrence, nature (MedDRA preferred term), time to onset, duration, seriousness criteria, relationship to vaccination, outcome, and whether the SAE led to early termination from the study, of SAEs throughout the study from Visit 1 (D0) to Visit 2 (D30 [+14 days]) after vaccination.

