5.4.2 Data handling conventions for safety variables

5.4.2.1 *Solicited Reactions*

Daily intensity

All daily records for solicited reactions will be derived into daily intensity according to the following classification: None, Grade 1, Grade 2, Grade 3, or Missing. The category of Unknown will be considered Missing if Unknown is recorded.

For the derivation of daily intensities, the following sequential steps will be applied:

1. Solicited reactions (except Fever/Pyrexia) with an investigator presence recorded as “No” and with all daily records missing then all daily intensities will be derived as None.
2. For a temperature partially missing after decimal point, the data will be analyzed replacing “MD” (missing data) by zero. For example, a “39.MD” daily temperature will be considered as “39.0°C” at the time of analysis.
3. For non-measurable (NM) solicited reactions, daily intensities will correspond to daily records reported in the clinical database. For measurable solicited reactions the daily measurements reported in the clinical database will be converted based upon the intensity scales defined in the protocol; this assumes a reaction that is too large to measure (NM) is Grade 3. Note the intensity could be considered “None” (not reaction) in the analysis despite being considered a reaction by the investigator (e.g., swelling measurement > 0 mm but < 25 mm in adults).

Note: The maximum intensity on the ongoing period is derived from the record of the maximum intensity/measurement after the end of the solicited period following the rule described above in “Daily intensity”.

Maximum overall intensity

Maximum overall intensity is derived from the daily intensities computed as described above in “Daily intensity” and is calculated as the maximum of the daily intensities over the period considered.

Presence

Presence is derived from the maximum overall intensity on the period considered:

- None : No presence
- Grade 1, Grade 2, or Grade 3 : Presence
- Missing : Missing presence

Subjects with at least one non-missing presence for a specific endpoint will be included in the analysis. Conversely, those without a non-missing presence will not be included in the analysis of the endpoint.

Time of onset

Time of onset is derived from the daily intensities computed as described above in “Daily intensity”. It corresponds to the first day with intensity of Grade 1, Grade 2, or Grade 3.

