5.4.4 Missing data

5.4.4.1 Safety

No replacement will be done. In all subject listings, partial and missing data will be clearly indicated as missing.

Immediate

For unsolicited non-serious systemic AEs, a missing response to the “Immediate” field is assumed to have occurred after the 30-minute surveillance period and will not be imputed.

For SAEs, missing or partially missing elapsed time from last vaccination recorded if within 24 hours will be assumed to have occurred after the 30-minute surveillance period and will not be imputed. Such SAEs will not be considered as immediate.

Causality

Missing causality (relationship) for unsolicited non-serious AEs and SAEs will be considered at the time of analysis as related to vaccination.

Measurements

Partially missing temperatures will be handled as described in “Daily intensity” of [Section 5.4.2.1](#).

Intensity

For solicited reactions, missing intensities will be handled as described in “Daily intensity” of [Section 5.4.2.1](#). For unsolicited non-serious AEs, missing intensities will remain missing and will not be imputed.

Start Date and Stop Date

Missing or partially missing start dates for unsolicited AEs will remain missing and not be imputed. If the start date is missing or partially missing, the time of onset will be considered to be missing. Nevertheless, unsolicited AEs with missing time of onset will be included in analyses according to the visit collected.

Missing or partially missing stop dates for AEs (solicited reactions and unsolicited AEs) will remain missing and not be imputed.

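### The Grade 1 threshold in SAP 5.4.2.4 drops ungraded AEs and SAEs that ended participation from the SOC/PT discontinuation table

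*SAP*

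**What the plan says.** SAP 5.4.2.4 starts from a complete source: "A flag is available in the clinical database for all AEs in order to identify AEs leading to discontinuation". It then sets three counting rules.

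- **Disposition table:** the reason on the termination form, alone.
- **Safety overview:** the reason on the termination form, or a flagged event on an AE page that is at least Grade 1 and in the period.
- **SOC/PT table:** "An event (solicited, unsolicited, or SAE) that has" the termination box "checked that is at least Grade 1 and is within the time period indicated". The termination form plays no part.

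Elsewhere the SAP defines what an event is. For unsolicited non-serious AEs (5.4.2.2): "An observation will be considered an event if it has at least a verbatim term and is not a Grade 0 intensity event". Missing is a category of its own, beside Grades 1 to 3. On absent grades (5.4.4.1): "For unsolicited non-serious AEs, missing intensities will remain missing and will not be imputed". Section 5.4.2.3, on SAEs, covers last vaccination, onset and duration, but not intensity.

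SAP Table 6 labels the two discontinuation rows as all and related AEs, within 30 days and over the whole study, with no grade limit. Protocol 9.2.2.2 has no grade limit either. It asks "whether the event led to early termination from the study, of unsolicited AEs up to Visit 2 after vaccination", and asks the same of SAEs, for which intensity is not among the listed attributes.

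**The concern.** The general AE tables keep an ungraded unsolicited AE, and the discontinuation table discards it. An AE that ended participation could thus appear by preferred term among the unsolicited AEs but not in the one table that names the events behind discontinuations. An ungraded SAE meets the same test, and the SAP has no rule to supply its grade.

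The error can only lower the count. The SAP's other missing-data rules go the other way: missing causality is treated as related (5.4.4.1), and an AE with missing onset stays in the tables (5.4.2.2, 5.4.2.3). Whether an event led to early termination is part of the secondary safety endpoints. With counts expected near zero, one event can be the whole result.

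**Working it through.** The documents give no figure for this rule, so there is none to reproduce. The check applies the stated conditions to the possible cases and then sizes one dropped event.

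**Step 1: which flagged, in-period events pass the SOC/PT rule.** Inputs are SAP 5.4.2.1 to 5.4.2.4 and 5.4.4.1, and the size scales in Protocol Tables 1 and 2 (Grade 1 starts above 0 mm at ages 2 to 9, and at 25 mm at ages 10 to 55).

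| Flagged event | Status elsewhere in the SAP | SOC/PT as written | With 'not Grade 0' |
|---|---|---|---|
| Unsolicited non-serious, Grade 1 to 3 | event | counted | counted |
| Unsolicited non-serious, grade missing | event | **not counted** | counted |
| Unsolicited non-serious, Grade 0 | not an event, listed only | not counted | not counted |
| SAE, Grade 1 to 3 recorded | event | counted | counted |
| SAE, no grade | event | **not counted** | counted |
| Local reaction 24 mm, age 10 or 30 | None, not present | not counted | not counted |
| Local reaction 24 mm, age 9 | Grade 1, present | counted | counted |

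Only the two bold cells conflict with the SAP's own status for the event.

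**Step 2: what each output shows for one subject with a flagged, ungraded, unsolicited AE.**

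| Termination form | Disposition | Overview | SOC/PT |
|---|---|---|---|
| Reason is Adverse Event | 1 | 1 | 0 |
| Another reason, AE page flagged | 0 | 0 | 0 |

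With the condition changed, the rows become 1, 1, 1 and 0, 1, 1.

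**Step 3: size of one dropped event.** The documents plan 180 per group; take that as the safety set (an assumption). The SAP uses Clopper-Pearson limits (5.4.7).

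- 0/180: upper limit = 1 − 0.025^(1/180) = 2.03%, so 0% (0 to 2.03%).
- 1/180 = 0.56%: lower limit = 1 − 0.975^(1/180) = 0.01%; upper limit = Beta(0.975; 2, 179) = 3.06%.
- 2/180 = 1.11% (0.13 to 3.96%), if two subjects were affected.
- With 171, the evaluable number in the power table's title: 0/171 is 0% (0 to 2.13%) and 1/171 is 0.58% (0.01 to 3.22%).

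**Step 4: how often it could arise.** Protocol 1.2.2.1 and 1.2.2.2 report no AE discontinuations with MenACYW in MET35 or MET43. With none among the 2,676 pooled MenACYW recipients that Protocol 1.2.2.2 gives as the denominator for immediate AEs in MET43, the rule of three gives an upper limit of 3/2,676 = 0.11%, or 180 × 0.0011 = 0.2 subjects per group. The event must also lack a grade.

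**The case against.** The strongest reply is that this will hardly ever happen. Protocol 9.2.2.3.3 requires intensity for each unsolicited AE, serious or not. The investigator must explain missing items (11.1), consistency checks look for omissions (11.2), and queries close before database lock (13.4.1). Protocol 5.2.11 lists Adverse Event first among termination reasons, so a correctly completed form keeps the subject in the disposition table and the overview. The three outputs are also built on different bases by design, and the safety analysis is descriptive. All of this stands and limits the size of the point. It does not reconcile a rule that drops ungraded events with a definition that keeps them.

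Three stronger readings are tempting, and the documents do not support them.

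- *That flagged local reactions under 25 mm at ages 10 to 55 are wrongly excluded.* SAP 5.4.2.1 says openly that such a measurement may be None "despite being considered a reaction by the investigator", and derives presence from intensity. The reaction is absent from the solicited tables too, so its absence here is consistent. The contrast with children comes from the protocol's two scales. Counting None would put into the discontinuation table a reaction that the same report treats as not present.
- *That the subject disappears from the report.* This happens only if the AE page is flagged and the form gives another reason.
- *That Protocol 5.2.9 creates Adverse Event terminations with no AE behind them.* It says "The Investigator must determine whether voluntary withdrawal is due to safety concerns", but it does not say that this applies where no AE occurred, and 5.2.11 defines the reason as termination because of an AE. The two sections can be read together.

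**Conclusion.** The point holds for flagged unsolicited AEs with a missing grade and for flagged SAEs without a grade. As written, they fail the SOC/PT rule and the AE-page route into the overview, although the SAP treats them as events and Table 6 announces all of them. The effect falls mainly on the SOC/PT table: one affected subject changes it from 1/180 to 0/180, assuming 180 per group in the safety set. Cases should be rare, and the primary immunogenicity inference is untouched. This is a small inconsistency worth correcting because it can only under-report and is cheap to remove. The conclusion rests on reading the threshold literally. The SAP introduces these rules as general ones but names no exception for a missing grade.

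**What to change.** In SAP 5.4.2.4, in both the safety overview rule and the SOC/PT rule, replace the requirement of at least Grade 1 with a requirement that the event is not Grade 0 (None). Flagged events with a missing grade, and all flagged SAEs, then count, with the grade shown as Missing where it applies. This matches the definition of an event in 5.4.2.2.

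Keep the convention that measurements below the Grade 1 size are None. No change to Protocol 5.2.9 is needed.

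The cost is a wording change in two rules and one programming condition. No new data or CRF change is required.
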